### **8.3.2 严重不良事件**

对于严重不良事件，研究者必须立即采取行动：

立即通知申办方的相应负责人，发送有签字和天期的病例报告表中的相应页给申办方的相应负责人，附加所有检查的复印件和这些检查完成的天期。应确保患者隐私得到保护，确保在提供给申办方的临床原始资料的复印件中去除患者的身份信息。实验室结果应包括正常范围值。

对任何严重不良事件的随访应该在该事件发生后一周内完成。并将严重不良事件填写在 CRF 相应位置，签字后最好以传真的方式报告给监测中心，监测中心的名称，地址，传真号将在临床试验方案中注明。

### **8.3.3 随访**

研究者应采取所有合理的措施来确保患者的安全。研究者应该追踪任何有关不良事件的结果（临床症状、体征、实验室检查结果等），直到患者恢复正常或病情稳定。

如果出现任何严重不良事件，研究者应追踪患者，直到临床症状完全缓解且实验结果恢复正常或直到病情稳定后。

这意味着在患者退出临床试验后随访仍将继续。监查团队有可能要求额外的研究。

在研究药物终止后，研究者应注意任何时间出现的任何严重不良事件。

## 9 研究流程

### 9.1 第一天访视=筛选+入组+基线访视

#### 9.1.1 筛选和入组

将核实入选，排除标准，并且：

对筛选对象进行 ABCD 评分（针对 TIA 患者）和神经系统评估（mRS 和 NIHSS 评分）。

对筛选对象进行 12 导联心电图检查以排除房颤。进行头 CT 或 MRI 检查以排除出血、血管畸形、肿瘤或脓肿。由于心电图和脑影像学检查被常规推荐用于所有 TIA 和小卒中患者，本研究将不提供这些费用。

研究者应完成包括所有筛选对象在内的一份筛选表。这些筛选表用来决定不同患者群是否具有代表性及确认分中心的参与。

患者将收到完整的研究相关信息，包括口头及书面的。

符合入组标准而不符合排除标准的患者将被邀请参加本研究。在入组之前患者应签署知情同意书。

#### 9.1.2 基线期评估

基线期评估包括：患者的人口学信息、本次脑血管事件的症状、服药史、既往史、家族史、吸烟饮酒史、体检结果、治疗前 mRS。

将对筛选对象进行实验室检查：血肌酐、血糖、中性粒细胞计数、白细胞计数、血小板计数、凝血象等。

将对筛选对象进行查体：体重、生命体征（卧位收缩压/舒张压/心率）。

将使用标准化仪器记录筛选对象的脑影像学检查、心电图检查结果。

### 9.1.3 随机化

统计学家将制定一份专业的随机表，确保治疗药物在每一个参与中心平均分布。如果患者同意参与试验，研究者将根据患者入组的先后顺序取得对应随机号，该随机号将记录在入组筛选表及 CRF 表上。

### 9.1.4 第 1 天的治疗

患者将收到第 1 天的研究药物，将被指导如何服用研究药物。研究药物首次服用的时间将被记录。

研究药物应在随机分组后尽快使用（在随机化后 1 小时之内）。

研究者将酌情给予阿司匹林剂量（第一天总剂量在 75-300mg 之间）。

将收集每位患者的以下信息：

- ◇ 人口学信息（年龄、性别、种族）；
- ◇ 患者服药史及伴随疾病；
- ◇ 合并用药
- ◇ 下次访视时间（随机化第  $21 \pm 2$  天）

## 9.2 21 天随访=第 $21 \pm 2$ 天

这次访视期间：

- ✓ 进行神经系统检查（mRS 和 NIHSS 评分）；
- ✓ 进行查体：体重、生命体征（卧位收缩压、舒张压、心率）；

- ✓ 应收集自上次随访以来合并用药及不良事件的信息；
- ✓ 收集整个研究过程中（第1天，第2天到第21±2天）第1个盒子中未服用的药物，用以判断用药量及评价患者的依从性；
- ✓ 研究者将从第2个药盒中发放给患者第22±2天到第90±7天的药物，并且指导患者从本次随访到下次随访期间如何服药
- ✓ 与患者预约下一次随访时间（随机化后90±7天）

### **9.33 个月随访=第 90±7 天**

注意：第 21 天和第 3 个月之间随访的天数不应超过 75 天

本次随访期间：

- ✓ 如果患者被诊断为症状性颅内大动脉狭窄（sICAD），应强烈建议完成其MRI+MRA序列（MRI序列包括T1+T2+DWI+FLAIR+T2\*）检查。所有图像应用DICOM格式保存，DICOM光盘将被传递到中心影像评价实验室；
- ✓ 进行神经系统检查（mRS和NIHSS评分）；
- ✓ 生存质量评价（EQ-5D量表）（见附表4）；
- ✓ 进行查体：包括生命体征（左侧收缩压、舒张压、心率）；
- ✓ 应收集自上次随访以来合并用药及不良事件的信息；
- ✓ 收集整个研究过程中治疗盒中未使用的药物，用来计算用药量及评价患者的依从性。

### **9.4 主要有效性终点事件访视**

如果患者发生可疑的神经系统临床症状，包括原缺血脑血管病恶化，出现新的短暂的或持续的神经系统症状。分

中心将在事件发生72小时内提交事件判读资料。包括以下内容：

- ✓ 进行神经系统检查（mRS和NIHSS评分）；
- ✓ 进行查体：包括生命体征（左侧收缩压、舒张压、心率）；
- ✓ 如果患者被诊断为症状性颅内大动脉狭窄（sICAD），应强烈建议完成其MRI序列（MRI序列包括T1+T2+DWI+FLAIR+T2\*）检查。所有图像应用DICOM格式保存，DICOM光盘将被传递到中心影像评价实验室；
- ✓ 如果患者发生新的可疑心脏病事件，要进行心脏评估（包括心电图检查）。如果有支持心肌梗死的临床信息需要及时收集并在72小时内上报给CRO以进一步判读；
- ✓ 应收集自上次随访以来合并用药及不良事件的信息。

## 10 统计学方案

### 10.1 统计分析方案

这部分是统计学分析的概述。完整的详细描述请见统计分析计划书（SAP）。它对如何收集数据和在临床研究报告中陈列数据进行了总体规定。最终版的 SAP 将会数据库锁定和揭盲前出版。SAP 将规定所有“预先规定的、计划进行的分析”。

#### 10.1.1 样本量估算

##### 10.1.1.1 主要无效假设

在 TIA 和小卒中患者症状出现 24 小时内使用 3 个月氯吡格雷（起始剂量 300mg）合并前 21 天使用阿司匹林（75mg/天）与单独使用阿司匹林（75mg/天）90 天随访时发生主要终点事件（缺血性卒中和出血性卒中）的风险无差异。

本试验的最小样本量由试验预期的最小需求决定，也就是试验组与安慰剂组的出现具有临床意义的差异所需要的最小样本量。相对危险度降低 22%（氯吡格雷相对危险度是 0.78）是我们期望达到的最低程度的差异标准。

预计如果样本量达 5100 人，在双侧检验  $\alpha = 0.05$  的条件下，我们有 90% 的把握可观测到相对危险度降低 22%，但有 5% 脱落率（药物依从性差）（图 2 和表 2）。样本量公式基于通常的两组对比人数量求得。公式会给我们需要做的生存分析保守的样本量估计值。

表 2. 对于对照组结果的不同风险 (12% 到 17%) 来计算样本量大小

机率	n 脱落	5%脱落	治疗组 结局风险	对照组 结局风险	氯吡格雷的 相对危险度
0.8	2880	3024	13%	17%	0.78
0.8	3094	3249	12%	16%	0.78
0.8	3334	3501	12%	15%	0.78
0.8	3608	3788	11%	14%	0.78
0.8	3926	4122	10%	13%	0.78
0.8	4296	4511	9%	12%	0.78
0.9	3856	4049	13%	17%	0.78
0.9	4140	4347	12%	16%	0.78
0.9	4462	4685	12%	15%	0.78
0.9	4830	5072	11%	14%	0.78
0.9	5254	5517	10%	13%	0.78
0.9	5750	6038	9%	12%	0.78

[figure not shown]

图 2. 对于对照组结果的不同风险 (90%或 80%概率) 来计算样本量大小

#### 10.1.1.1.1 安慰剂组 (单用阿司匹林组) 终点事件的风险

根据北加州和牛津的队列研究和 FASTER 预试验的数据, 在 TIA 高危患者 (ABCD 评分>4) 或小卒中患者症状出现 24 小时内给予阿司匹林治疗, 90 天卒中复发风险约为 14%。

表 3. 安慰剂组 (ASA) 结果的风险估计

人群	例数	3 个月风险	
		卒中	卒中 / 心肌梗死 / 死亡

所有 TIA 	2776	10.30%	12.14%
除去极小可能的 TIA 	2325	11.87%	14.02%
TIA 患者的 ABCD  评分 			
> 3	2067	12.58%	14.42%
> 4	1379	14.72%	16.75%
> 5	737	17.50%	19.94%
TIA and minor stroke 	194	10.8%	11.9%

 基于北部加州和牛津夏州的 cohort 研究数据库

 FASTER 试验

#### 10.1.1.1.2 氯吡格雷与阿司匹林联用的相对危险度

我们预期氯吡格雷在未联合应用阿司匹林的情况下可以降低复合终点事件（卒中、心肌梗死和心血管死亡）的风险。在 FASTER 试点试验中氯吡格雷组对比安慰剂组相对危险度降低达 34.3%（对于所有卒中），但是由于样本量过小，置信区间太宽，该数据无统计学意义。

[figure not shown]
在入组标准更宽的亚组试验分析中，我们可以得到更多的 RRR 估计值，并且在长期的治疗中，药物的残留风险也可以变得更低。

在 CHARISMA 试验中，卒中/TIA 患者在卒中/TIA 发生后 21 天内联合应用氯吡格雷/阿司匹林比单独应用阿司匹林的相对危险度降低 24%。在 MATCH 试验中，卒中/TIA 患者在 MATCH 试验中，卒中/TIA 患者在卒中/TIA 发生后 7 天内联合应用氯吡格雷/阿司匹林对比单独应用氯吡格雷的相对危险度降低达 17%。基于之前的安全性结果，我们不认为 TIA

患者使用氯吡格雷将导致大量颅内出血或危及生命的出血。因此，上述实验的综合结果是使用氯吡格雷带来的明显收益并不被增加的颅内出血风险所抵消。根据这些之前的研究，我们推测相对危险度降低将大于 22%。(图 3)

图 3. 临床事件不同时间窗联合应用氯吡格雷/阿司匹林对比单独应用氯吡格雷/阿司匹林

(终点事件: 卒中、心肌梗死、血管性死亡)

#### 10.1.1.1.3 相对危险度的临床意义

样本量的大小取决于检测到相对危险度降低 22% 的需求。基于该数据，32 名 TIA/小卒中的患者(不考虑其他危险因素)中经治疗后预期 3 个月时卒中复发事件将减少。这种效果在临床上被治疗医生所重视，在二级预防中，联用氯吡格雷/阿司匹林比单独应用阿司匹林能给患者带来更大收益。

#### 10.1.1.1.4 症状发生与入组之间的间隔 t

由于入组延误，卒中很可能在患者随机化入组前发生。在 TIA 症状发作 24 小时内发生重大事件的患者应该从事件发生率的分析中剔除，因为许多这样的患者在终点事件发生之前还没有入组和接受治疗。

#### 10.1.1.1.5 失访

这些计算结果允许 5% 的中途脱落率（药物非依从性）。

#### 10.1.1.1.6 把握度与 $\alpha$ 值

一个不确定的假设用来推测有效性及事件发生率，我们选择一个样本量来提供 90% 的把握或机率（双侧检验， $\alpha$  等于 5%）。总之，每组大约 2550 患者（样本总数 5100）有 90% 的概率检测到相对危险度降低 22%，双侧检验  $\alpha$  等于 0.05，并且 5% 脱落信息（药物非依从性）（表 2，图 2）。（增加氯吡格雷后相对危险度（RR）是 0.78）。

## 10.2 统计分析

详细的统计分析计划将在试验启动期制定，包括所有分析的表格和细节。

### 10.2.1 主要终点事件

主要分析采用意向性治疗分析方法，包括接受首次研究药物的受试者。缺失值将仍然按缺失对待，患者在最后一次随访时将接受检查（临床事件的时间，研究结束时，或在失访前的最后一次随访时）。我们将用 Kaplan-Meier 曲线模拟 90 天随访时的卒中（缺血性或出血性）的累积风险，使用 Cox 比例风险模型计算风险比例和 95% 可信区间，使用 Log-rank 检验评估疗效。所有统计数据都将采用双侧检验， $P < 0.05$  被认为有统计学意义。

### 10.2.2 次要终点事件

多数次要结局分析也将采用主要结局分析策略。对于连续性变量（如成本和 MOCA），我们将使用多元线性回归分析。连续变量将检查大致正常和异方差残差和离群。转换和/或加权最小二乘法将被视为补救措施的非正常和异方差。转换和/或加权最小二乘法将被视为补救措施。极端值进行有效性检查，将对结论进行灵敏度分析。

## 11 伦理及调控规程

### 11.1 伦理原则

本临床试验遵循第 18 届世界医学宣言（赫尔辛基，1964），所有应用修正案将在第 18 届世界医学宣言和 ICH 指南

中的药品临床试验管理规范指导下展开。

## **11.2 法律法规**

本临床试验管理将遵循国际法律法规，并遵循试验所在地中国的法律法规以及任何有关应用的指导方针。

## **11.3 知情同意书**

研究者(根据相应法规的要求)或由研究者授权并负责的人员，应该充分告知受试者包括伦理委员会许可的书面信息在内的临床试验的所有相关问题。研究者应该用受试者可以理解的语言或术语最大程度的告知其有关研究的信息

在参与临床试验之前，患者本人或其法定代表应与患者讨论知情同意的研究人员共同签署知情同意书（姓名及天期）。研究者应向患者提供已签署的知情同意书的复印件。

在递呈给伦理委员会审核之前，研究者所使用的知情同意书应由资助方审阅并批准。

## **11.4 审查机构/独立的伦理委员会(IRB/IEC)**

在试验开始前，研究者或申办方必须向伦理委员会递交临床试验方案，研究者须向申办方递交伦理委员会签署书面的同意意见的复印件。

临床试验（研究编号、研究方案名称、版本号），审阅过的文件（包括临床研究方案、知情同意书、研究者操作手册、研究者简历等），投票成员的资格认定及审阅天期等都应清楚地记录在伦理委员会同意书上

在试验开始之前研究药物不得向研究中心发放，在直到获得申办方收到并注明签署天期的书面同意书的复印件前临床研究不得开始。

在临床试验过程中，对所有试验方案的任何修改应向伦理委员会报告，经批准后方可执行。在试验中发生的任何可能影响患者安全或临床试验继续展开的事件，尤其是安全性的改变均应向伦理委员会报告。研究者操作手册的更新应递交给伦理委员会。

如果需要，每年应向伦理委员会递交临床试验的进展报告和临床试验结束后的临床结果摘要。

## **12 研究监查**

### **12.1 研究者职责**

研究者保证在进行临床试验时遵循临床试验方案，遵循 ICH 指南中的药品临床试验管理规范以及相应法律法规。

研究者应保证遵循临床试验方案中的和由申办方提供的所有研究操作（包括安全性原则）。研究者应根据相关要求，以一种准确、清晰的方式（病例报告表[CRF]、偏差解析表[DRF]及其它方式）提供可靠数据和临床试验方案要求的所有信息，并确保申办方代表可直接查看原始资料。

研究者可能会任命他/她认为合适的人作为协助研究者。协助研究者将根据临床试验方案协助进行临床试验的管理。所有的协助研究者将被及时任命并记录。协助研究者接受研究者的监督和管理。研究者将提供给他们一份临床试验方案和所有必需的信息。

临床试验的申办方对卫生当局负责，通过采取所有适当的手段来确保临床试验的合理管理，这些手段如伦理、临床试验方案依从性、记录在病例报告中数据的完整性和有效性等。因此，监查团队的主要责任是帮助研究者和申办方保证临床试验各个方面的高度的伦理性、科学性、专业性和规范性。

监查团队将定期通过现场访视、信件或电话形式与每个中心联系，将派出代表来评估研究进展、研究者和患者对临床方案的依从性以及解决紧急的问题。在这些监查访问中，监查员将和研究者共同监查，要点如下（并非无遗漏）：患者的知情同意、患者的招募和随访、严重不良事件文件的记录和报告、研究药物发放、研究药物组患者的依从性、研究药物计数，伴随治疗和数据的质量。

### **12.2 原始数据要求**

根据 ICH 指南中的 GCP 原则，监督团队应对照原始资料来核查 CRF。知情同意书将包括一个声明，即患者允许已授权的申办方、伦理委员会、权威机构直接查阅病例报告表上相关的原始资料（如患者的医疗档案、预约记录、原始实

验室记录等)。上述人员应遵循职业保密规定, 必须对患者的所有个人信息或医疗信息保密。

### **12.3 病例报告表(CRF)的使用、完成及附加要求**

研究者有责任保证恰当、正确填写 CRF, 记录(根据资助方的指示)所有的观察和相关临床研究的其它数据。所有的 CRF 应该以一种整洁的、清晰的方式完整的完成, 从而确保数据被正确解释。

如果信息需要修改, 不应进行涂改或覆写, 正确的信息应写在原始信息旁边, 并由修改人签名及注明天期。

CRF 将分为两份, 一份保留在分中心, 一份递交给申办方。

申办方收到 CRF 后进行计算机数据分析, 可能会产生额外需求, 研究者必须通过证实或修改数据的方式来回答这些需求。更正的内容将通过研究者和申办方附加到 CRF。

### **12.4 计算机化系统应用**

电脑系统用于建立, 修改, 维护, 存档, 检索和传输数据(包括 IVRS, 监测工具, 数据录入和统计分析)。

## **13 研究结果公布**

执行委员会将按照管理条例和程序来公布该试验的结果。数据库锁定后试验结果将尽快被公布。

在 5100 例 TIA 或小卒中患者研究人群中, 本试验将对其治疗效果、医疗措施及临床结局进行详细地资料分析。当然, 被咨询的 CHANCE 生物统计学专家是不可能识别出此试验的任何患者; 这就可能要求去除或整合一些特定的统计学变量; 同时, 访问数据集也不需要提供数据使用协议。最后, 以逗号分隔的文本格式的磁盘存储数据(包括文本格式的数据字典)将送至有合作意向的第三方机构处理。

## **14 辅助研究**

辅助研究方案将由执行委员会审查。因为需要收集额外的研究数据, 不强行要求, 但是鼓励分中心参加这些辅助研究。执行委员会将按照管理条例和程序来公布该试验的结果。

## 16 附件:

### 附表 1. 终点事件定义

卒中	
突然发生的局灶性神经系统症状及体征，与脑循环障碍相关。
 
将根据 SSS-TOAST 标准进行病因分型。

缺血性卒中	
急性局灶性脑或视网膜梗死。标准：(1) 急性发作的新的局灶性神经功能缺损的临床征象或影像学证据持续时间超过 24 小时，排除其他非缺血性病因（如脑部感染，脑外伤，脑肿瘤，癫痫，严重的代谢性疾病或退行性神经系统疾病）；或(2) 急性脑或

	
视网膜缺血事件，排除其它非缺血性病因，局灶症状或体征持续时间小于 24 小时，但伴有影像学上新发梗死灶证据；或(3)原有血管源缺血性卒中进展（即在原发缺血性卒中基础上 NIHSS 增加 <math>\geq 4</math>，不包括梗塞后出血转化或症状性颅内出血）持续时间大于 24 小时，伴有头 MRI 或 CT 上的新的缺血性改变。

出血性卒中
	
突发的血液渗出至脑实质或蛛网膜下腔引起的神经系统症状。脑梗死出血转换将归为脑梗死其中一类。

TIA
	
急性发作的局灶性脑或视网膜缺血，持续时间小于 24 小时，影像学上不存在脑梗死证据。排除其他非缺血性病因（如脑部感染，脑外伤，脑肿瘤，癫痫，严重的代谢性疾病或退行性神经系统疾病）。

症状性脑出血
	
血液破入至脑实质并伴有临床神经功能恶化，恶化的定义为 NIHSS 增加大于等于 4 分，或者由神经功能恶化导致的死亡。脑出血定义为急性的血液破入脑实质。脑出血诊断标准：影像学检查、手术或尸检证实存在脑实质内血肿。

非症状性脑出血
	
血液破入至脑实质不伴有临床神经功能恶化。脑出血诊断标准：影像学检查、手术或尸检证实存在脑实质内血肿。

其他症状性颅内出血
	
血液破入颅内并伴有神经功能恶化。神经功能恶化定义为 NIHSS 增加大于等于 4 分，或者由神经功能恶化导致的死亡。颅内

	
出血定义为血液破入蛛网膜下腔、硬膜外或硬膜下并伴有临床症状，其断标准：影像学检查、手术或尸检证实存在蛛网膜下腔、硬膜外或硬膜下血肿。

其他非症状性颅内出血	
血液破入颅内不伴有神经功能恶化。颅内出血诊断标准：影像学检查、手术或尸检证实存在蛛网膜下腔、硬膜外或硬膜下血肿。

心肌梗死后冠状动脉再通治	
存在心肌梗死的证据，并给与冠状动脉再通治疗。心肌梗死诊断采用国际通用标准(Circulation 2007 116:2634-2653)，参考心脏标记物、心电图（ECG）、临床表现、影像检查和病理检查 5 项诊断指标。

心肌梗死后无冠状动脉再通治	
存在心肌梗死的证据，未给与冠状动脉再通治疗。心肌梗死诊断采用国际通用标准(Circulation 2007 116:2634-2653)，参考心脏标记物、心电图（ECG）、临床表现、影像检查和病理检查 5 项诊断指标。

冠状动脉再通治非心肌梗死性冠状动脉疾病	
治疗非心肌梗死的冠状动脉疾病而进行的增加冠状动脉血流量的手术。包括：冠状动脉造影、支架植入术或冠状动脉搭桥术。

缺血性血管源性死亡	
由缺血性卒中、心肌梗死、心律失常、肺动脉栓塞、肠或肢体梗死导致的死亡；突发心源性死亡或不能排除由非缺血性原因导致的死亡。

出血性血管源性死亡	由颅内或系统性出血导致的死亡。
-----------	-----------------

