#### 4.6.2 Secondary Efficacy Endpoint

- Percentage of composite of any stroke, myocardial infarction, and vascular death within 3 month.
- Patients with the 3-month new clinical vascular events (ischemic stroke/ hemorrhagic stroke/ TIA/ MI/ vascular death) evaluated individually.
- Modified Rankin Scale score changes (continuous) and dichotomized at percentage with score 0-2 vs. 3-6 at 3 month follow-up (Scale is described in Appendix 2).
- Further efficacy exploratory analysis:
  - ✧ Impairment (changes in NIHSS scores at 3 month follow-up), (Scale is described in Appendix 3).
  - ✧ Quality of Life (EuroQol EQ-5D scale, described in Appendix 4).
- Efficacy endpoint will also be analyzed stratified by etiological subtypes (non-ICAD vs. ICAD), by time randomization (< 12 hours vs. ≥ 12 hours), by qualifying event (TIA vs. minor stroke), and by age (<65 years vs. ≥65 years).

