#### **Secondary Efficacy**

- Rate of the composite outcome: including any stroke, myocardial infarction, and vascular death as a cluster and evaluated individually

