### Secondary Efficacy Analyses

#### **Rate of combined vascular events during the 3-month treatment period**

The rate of combined vascular events occurring during the treatment will be analyzed using a Cox proportional hazard model similar to that in the previous section, with the pooled study center as a random effect. A combined vascular event was defined as any of the 4 following events: ischemic stroke, hemorrhagic stroke, myocardial infarction, or death from cardiovascular causes. This will also be presented graphically on a Kaplan-Meier plot.

Each of the 4 vascular events will also be analyzed using the same method and the event rate for each event will be calculated for each treatment group.

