
Ischemic vascular death
	
Death due to ischemic stroke, myocardial infarction, sudden cardiac death, arrhythmia, pulmonary embolism, bowel or limb infarction, or any death not readily attributable to a non-ischemic cause

Hemorrhagic Vascular death
	
Death due to intracranial or systemic hemorrhage

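### The Chinese protocol reverses the residual clause for ischemic vascular death, and the SAP's analysis paragraph uses an undefined term for the death component of the secondary composite

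*Supplement*

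**What the plan says.** **The endpoint.** Section 4.6.2 of the final English protocol gives the secondary composite as "Percentage of composite of any stroke, myocardial infarction, and vascular death within 3 month". The final SAP, under Secondary Efficacy, has it "including any stroke, myocardial infarction, and vascular death as a cluster and evaluated individually". Neither place defines vascular death. The only definitions are the two entries in Appendix 1 of each document, ischemic and hemorrhagic.

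**Ischemic vascular death.** The English protocol and the SAP list named ischemic causes and then add "any death not readily attributable to a non-ischemic cause". The final Chinese protocol (附表 1) has a similar list but ends with "突发心源性死亡或不能排除由非缺血性原因导致的死亡". In translation: sudden cardiac death, or a death for which a non-ischemic cause cannot be excluded.

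**Hemorrhagic vascular death.** All three texts agree. The English protocol and the SAP say "Death due to intracranial or systemic hemorrhage"; the Chinese protocol says "由颅内或系统性出血导致的死亡".

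**The analysis.** The SAP section on the rate of combined vascular events builds the composite from four events, the last three being "hemorrhagic stroke, myocardial infarction, or death from cardiovascular causes". It adds that each of the four is also analysed on its own by the same Cox model. The SAP's objectives, endpoint list and subgroup section all say vascular death instead.

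**The concern.** Two things could make the same death count differently depending on which text is followed.

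First, the residual clauses point in opposite directions. In English, a clear non-ischemic cause takes a death out of the category. In Chinese, read literally, the same fact puts it in. A pre-specified secondary outcome should not depend on the language version in the adjudicator's hand.

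Second, the paragraph from which the composite will be programmed uses a label that appears nowhere else in the SAP and is not tied to Appendix 1. A programmer could reasonably leave out a fatal gastrointestinal bleed under that label, although Appendix 1 counts it.

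At stake are the secondary composite and, more directly, vascular death as a separate result. Deaths unrelated to treatment, added at similar frequency to both arms, pull the estimated effect toward no difference.

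**Working it through.** No figure in the plan depends on the death definition, so there is none to reproduce. The sample size rests on stroke alone (14% against 0.78 × 14% = 10.92%) and is not touched. The check is a comparison of texts, followed by a bound on size.

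**1. Four kinds of death under each text**

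| Death | English protocol and SAP Appendix 1 | Chinese Appendix 1, literal | SAP analysis paragraph |
|---|---|---|---|
| Myocardial infarction or ischemic stroke | vascular | vascular | composite event already |
| Cause unknown | vascular (residual clause) | vascular (residual clause) | not stated |
| Day 40, clear pneumonia | not vascular | vascular | not stated |
| Day 15, gastrointestinal bleed | vascular (hemorrhagic entry) | vascular (hemorrhagic entry) | unclear |

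The Chinese and English texts agree on deaths of unknown cause. They part on deaths with an established non-ischemic cause: such a cause plainly cannot be excluded, so the Chinese clause is met. With the listed ischemic causes and the hemorrhagic entry added, almost every death qualifies. Yet the Chinese protocol lists total mortality as a separate outcome (sections 3.2.5 and 4.6.3.4).

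**2. Ceiling on what a death definition could move in the composite**

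Inputs: protocol Table 3 (3-month stroke; stroke/MI/death) and about 2,550 patients per arm (section 10.1.1.1.6). Formula: the difference between the two rates is MI or death without stroke.

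- TIA cohort, ABCD2 > 3: 14.42 − 12.58 = 1.84 points; 2,550 × 0.0184 = 46.9, about 47 per arm; 1.84/14.42 = 12.8% of the composite.
- TIA cohort, ABCD2 > 4: 16.75 − 14.72 = 2.03 points; about 52 per arm; 12.1%.
- Pilot trial: 11.9 − 10.8 = 1.1 points; about 28 per arm; 9.2%.

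These are upper bounds. They include MI and undisputed vascular deaths.

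**3. Dilution of the composite ratio by added non-vascular deaths**

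Assumptions: control risk 14.42%, true ratio 0.78, and a proportion x of each arm with an added non-vascular death. The documents give no value for x, so a range is shown.

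Ratio = (0.78 × 0.1442 + x) / (0.1442 + x)

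- x = 0.002: 0.114476/0.1462 = 0.783
- x = 0.005: 0.117476/0.1492 = 0.787
- x = 0.008: 0.120476/0.1522 = 0.792

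Table 3's column is headed death, not vascular death, so these deaths may already sit inside the 14.42%. The ratio is then 0.78 + 0.22x/0.1442, which is 0.783 at x = 0.002 and 0.792 at x = 0.008. The ends of the range are unchanged to three decimals.

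**4. Vascular death on its own**

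If a share f of all deaths has a clear non-vascular cause (assumed), the literal Chinese rule multiplies the count by 1/(1 − f): 1.25 at f = 0.2 and 2.00 at f = 0.5. This restates the assumption as a count. It shows how exposed the component is and does not estimate what will happen.

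**The case against.** **The Chinese clause is probably a translation slip.** The ischemic-stroke row of the same table uses the verb for exclude in its proper sense, requiring that non-ischemic causes be ruled out. A literal reading of the death row defeats its own title. The protocol assigns the pre-specified analyses to the SAP, whose Appendix 1 has the expected clause. Deaths go to an expert committee with its own charter, which is not among the documents. All of this is fair, and nothing shows that anyone would classify a pneumonia death as vascular. But it does not remove the problem. All centers are in China, the adjudication committee has members inside and outside mainland China, and no text says which language version governs. The clause is a stated endpoint rule, and followed as written it misclassifies deaths.

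**The SAP label may simply be a synonym.** The paragraph's heading speaks of vascular events, its four items match the list in the subgroup section, and the SAP's only death definitions are those in Appendix 1. This stands. A reader might infer that the label excludes every fatal systemic bleed and so hides a harm of treatment. The documents do not support that. No sentence excludes such deaths, and they would in any case appear in the bleeding safety endpoint, which includes fatal bleeding, in total mortality, and in the Cox model for death from any cause. Fatal intracerebral or subarachnoid bleeding enters the composite as hemorrhagic stroke. What remains is an ambiguity.

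**The size is small and assumed.** For the composite, this also stands.

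**Conclusion.** The concern holds in two limited parts. The Chinese residual clause for ischemic vascular death reverses the one in the English protocol and the SAP, and read literally makes vascular death nearly the same as total mortality. The SAP analysis paragraph uses an undefined label, so it is unclear whether a fatal systemic bleed counts in the composite. It is not shown that the label drops such bleeds.

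The effect is confined to the secondary composite and its death component. For the composite it is small: 0.78 becomes about 0.783 to 0.792, assuming 0.2% to 0.8% added deaths per arm that treatment does not affect. Vascular death analysed alone could be affected materially, with a count 25% to 100% higher if 20% to 50% of deaths are non-vascular (assumed). The primary endpoint, sample size and power are unaffected. The correction should be made because a pre-specified outcome ought to have one definition.

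**What to change.** - In the Chinese Appendix 1, replace the residual clause with one that carries the English meaning, for example 不能明确归因于非缺血性原因的死亡.
- In the SAP section on combined vascular events, replace the cardiovascular-causes label with *vascular death (ischemic or hemorrhagic, Appendix 1)*, both for the composite and for the separate analysis of the component.
- Instruct the adjudication committee to apply that single definition.
- Check deaths already adjudicated, looking at those with a clear non-ischemic cause and those from systemic bleeding.

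The cost is two wording corrections and a short review of existing adjudications. No new data are needed.

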## 附表 2. 改良 Rankin 量表的评定方法

改良 Rankin 量表是用来衡量患者脑卒中后的功能恢复的结果。黑体字显示了每一级别的正式定义。斜体字则给予了进一步指导，以期减少不同观察者间可能产生的误差，但对面谈的架构没有要求。请注意仅考虑自脑卒中以后发生的症状。假如患者无须外界帮助，可在某些辅助装置的帮助下行走，则被视为能够独立行走。

如果两个级别对患者似乎同样适用，并且进一步提问亦不太可能做出绝对正确的选择，则应选择较为严重的一级。

### **0-完全没有症状**

尽管可能会有轻微症状，但患者自脑卒中后，没有察觉到任何新发生的功能受限和症状。

### **1-尽管有症状，但未见明显残障；能完成所有经常从事的职责和活动**

患者有由脑卒中引起的某些症状，无论是身体上或是认知上的（比如影响到讲话、读书、写字；或身体运动；或感觉；或视觉；或吞咽；或情感），但可继续从事所有脑卒中以前从事的工作、社会和休闲活动。用于区分级别 1 和 2（见下）的关键问题可以是，“是否有些事情你过去经常做，但直到脑卒中以后你不能再做？”。频率超过每月一次的活动被认为是“经常”。

### **2-轻度残障；不能完成所有以前能从事的活动，但能处理个人事务而不需帮助**

某些脑卒中以前可以完成的活动（如开车、跳舞、读书或工作），脑卒中后患者不再能够从事，但仍能每天照顾自己而无须他人协助。患者能够不需要别人的帮助穿衣、行走、吃饭、去卫生间、准备简单的食物、购物、本地出行等。患者生活无需监督。设想这一级别的患者可在无人照顾的情况下单独居家一周或更长时间。

### **3-中度残障；需要一些协助，但行走不需要协助**

在这一级别，患者可以独立的行走（可借助辅助行走的机械）能够独立穿衣、去卫生间、吃饭等，但是更复杂的任务需要在别人协助下完成。例如，需要他人代替完成购物、做饭或打扫卫生的工作，和一周不止一次看望患者以确保完成上述活动。需要协助的不仅是照顾身体，更多的是给予建议；比如，在这一级别的患者将需要监督或鼓励来处理财务。

### **4-重度残障；离开他人协助不能行走，以及不能照顾自己的身体需要**

患者需要其他人帮助打理日常生活，无论是行走、穿衣、去卫生间或吃饭。患者需要每天照看至少一次、通常是二次或更多次，或必须和看护者住得很近。为区分级别 4 和 5（见下），考虑患者是否能够在一天当中，常规单独生活适当的时间。

### **5-严重残障；卧床不起、大小便失禁、须持续护理和照顾**

虽然不需受过培训的护士，但需要有人整个白天和夜间数次照看。

## 附表 3. NIHSS 评分

注意每次 NIHSS 评分时要记录实际评定的时间按表评分，记录结果。不要更改记分，记分所反映的是病人实际情况，而不是医生认为病人应该是什么情况。快速检查同时记录结果。除非必要的指点，不要训练病人（如反复要求病人做某种努力）。

如部分项目未评定，应在表格中详细说明。

	检查	评分	分值
1a	意识水平： 即使不能全面评价（如气管插管、语言障碍、气管创伤、	0= 清醒，反应敏锐 1= 嗜睡，最小刺激能唤醒 病人完成指令、回答问	_____

	检查	评分	分值
	绷带包扎等), 检查者也必须选择 1 个反应。只在病人对有害刺激无反应时 (不是反射), 方记录 3 分。	题或有反应 2= 昏睡或反应迟钝, 需要强烈反复刺激或疼痛刺激才能有非固定模式的反应 3= 仅有反射活动或自发反应, 或完全没反应、软瘫、无反应	
1b	意识水平提问: (仅对最初回答评分, 检查者不要提示) 询问月份, 年龄。回答必须正确, 不能大致正常。失语和昏迷者不能理解问题记 2 分, 病人因气管插管、气管创伤、严重构音障碍、语言障碍或其他任何原因不能说话者 (非失语所致) 记 1 分。	0= 都正确 1= 正确回答一个 2= 两个都不正确或不能说	_____
1c	意识水平指令: 要求睁眼、闭眼: 非瘫痪手握拳、张手。若双手不能检查, 用另一个指令 (伸舌)。仅对最初的反应评分, 有明确努力但未完成也给评分。若对指令无反应, 用动作示意, 然后记录评分。对创伤、截肢或其他生理缺陷者, 应给予一个适宜的指令。	0= 都正确 1= 正确完成一个 2= 都不正确	_____
2	凝视: 只测试水平眼球运动。对自主或反射性 (眼头) 眼球运动记分。若眼球侧视能被自主或反射性活动纠正, 记录 1 分。若为孤立性外周神经麻痹 (III、IV、V), 记 1 分。在失语病人中, 凝视是可测试的。对眼球创伤、绷带包扎、盲人或有视觉或视野疾病的患者, 由检查者选择一种反射性运动来测试。建立与眼球的联系, 然后从一侧向另一侧运动, 偶尔能发现凝视麻痹。	0= 正常 1= 部分凝视麻痹 (单眼或双眼凝视异常, 但无被动凝视或完全凝视麻痹) 2= 被动凝视或完全凝视麻痹 (不能被眼头动作克服)	_____
3	视野: 用手指数或视威胁方法检测上、下象限视野。如果病人	0= 无视野缺失 1= 部分偏盲 2= 完全偏盲	_____

	检查	评分	分值
	能看到侧面的手指，记录正常。如果单眼盲或眼球摘除，检查另一只眼。明确的非对称盲（包括象限盲），记 1 分。病人全盲（任何原因）记 3 分，同时刺激双眼。若人濒临死亡记 1 分，结果用于回答问题 11。	3= 双侧偏盲（全盲，包括皮质盲）	

	检查	评分	分值
4	
面瘫:
 
言语指令或动作示意, 要求病人示齿、扬眉和闭眼。对反应差或不能理解的病人, 根据有害刺激时表情的对称情况评分。有面部创伤/绷带、经口气管插管、胶布或其他物理障碍影响面部检查时, 应尽可能移至可评估的状态。
	0= 正常 1= 最小 (鼻唇沟变平、微笑时不对称) 2= 部分 (下面部完全或几乎完全瘫痪, 中枢性瘫) 3= 完全 (单或双侧瘫痪, 上下面部缺乏运动, 周围性瘫)	_____
5	
上肢运动:
 
上肢伸展: 坐位 90°, 位卧 45°。要求坚持 10 秒; 对失语的病人用语言或动作鼓励, 不用有害刺激。评定者可以抬起病人的上肢到要求的位置, 鼓励病人坚持。仅评定患侧。
	0= 上肢于要求位置坚持 10 秒, 无下落 1= 上肢能抬起, 但不能维持 10 秒, 下落时不撞击床或其他支持物 2= 能对抗一些重力, 但上肢不能达到或维持坐位 90° 或位卧 45°, 较快下落到床上 3= 不能抗重力, 上肢快速下落 4= 无运动 9= 截肢或关节融合, 解释: _____	5a 左上肢 _____ 5b 右上肢 _____
6	
下肢运动:
 
下肢卧位抬高 30°, 坚持 5 秒; 对失语的病人用语言或动作鼓励, 不用有害刺激。评定者可以抬起病人的上肢到要求的位置, 鼓励病人坚持。仅评定患侧。
	0= 于要求位置坚持 5 秒, 不下落 1= 在 5 秒末下落, 不撞击床 2= 5 秒内较快下落到床上, 但可抗重力 3= 快速落下, 不能抗重力 4= 无运动 9= 截肢或关节融合, 解释: _____	6a 左下肢 _____ 6b 右下肢 _____

7	
共济失调: 目的是发现双侧小脑病变的迹象。实验时双眼睁开,若有视觉缺损,应确保实验在无缺损视野内进行。双侧指鼻、跟膝胫试验,共济失调与无力明显不呈比例时记分。如病人不能理解或肢体瘫痪不记分。盲人用伸展的上肢摸鼻。若为截肢或关节融合,记录9分,并解释清楚。
	
0= 没有共济失调 1= 一个肢体有 2= 两个及两个以上肢体有
	
_____

8	
感觉: 用针检查。测试时,用针尖刺激和撤除刺激观察昏迷或失语病人的感觉和表情。只对与卒中有关的感觉缺失评分。偏身感觉丧失者需要精确检查,应测试身体多处部位:上肢(不包括手)、下肢、躯干、面部。严重或完全的感觉缺失,记2分。昏迷或失语者可记1或0分。脑干卒中双侧感觉缺失记2分。无反应及四肢瘫痪者记2分。昏迷病人(1a=3)记2分。
	
0= 正常,没有感觉缺失 1= 轻到中度,患侧针刺感不明显或为钝性或仅有触觉 2= 严重到完全感觉缺失,面、上肢、下肢无触觉
	
_____

9	
语言: 命名、阅读测试。要求病人叫出物品名称、读所列的句子。从病人的反应以及一般神经系统检查中对指令的反应判断理解能力。若视觉缺损干扰测试,可让病人识别放在手上的物品,重复和发音。气管插管者手写回答。昏迷病人(1a=3),3分,给恍惚或不合作者选择一个记分,但3分仅给哑人或一点都不执行指令的人。
	
0= 正常,无失语 1= 轻到中度:流利程度和理解能力有一些缺损,但表达无明显受限 2= 严重失语,交流是通过病人破碎的语言表达,听者须推理、询问、猜测,能交换的信息范围有限,检查者感交流困难 3= 哑或完全失语,不能讲或不能理解
	
_____

10	
构音障碍: 不要告诉病人为什么做测试。读或重复附表上的单词。若病人有严重的失语,评估自发语言时发音的清晰度。若病人气管插管或其他物理障碍不能讲话,记9分。同时注明原因。
	
0= 正常 1= 轻到中度,至少有一些发音不清,虽有困难,但能被理解 2= 言语不清,不能被理解 9= 气管插管或其他物理障碍,解释: _____
	
_____

11	
忽视症： 若病人严重视觉缺失影响双侧视觉的同时检查，皮肤刺激正常，则记分为正常。若病人失语，但确实表现为关注双侧，记分正常。通过检验病人对左右侧同时发生的皮肤感觉和视觉刺激的识别能力来判断病人是否有忽视。把标准图显示给病人，要求他来描述。医生鼓励病人仔细看图，识别图中左右侧的特征。如果病人不能识别一侧图的部分内容，则定为异常。然后，医生请病人闭眼，分别测上或下肢针刺觉来检查双侧皮肤感觉。若病人有一侧感觉忽略则为异常。
	
0= 没有忽视症 1= 视、触、听、空间觉或个人的忽视；或对任何一种感觉的双侧同时刺激消失 2= 严重的偏身忽视；超过一种形式的偏身忽视；不认识自己的手，只对一侧空间定位
	
_____

总分			
_____

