### **5.2 Study Population**

#### Inclusion Criteria

- Adult subjects (male or female  $\geq 40$  years)
- Acute non-disabling ischemic stroke (NIHSS  $\leq 3$  at the time of randomization) that can be treated with study drug within 24 hours of symptoms onset. Symptom onset is defined by the “last seen normal” principle.
- TIA (Neurological deficit attributed to focal brain ischemia, with resolution of the

deficit within 24 hours of symptom onset), that can be treated with study drug within 24 hours of symptoms onset and with moderate-to-high risk of stroke recurrence (ABCD2 score  $\geq 4$  at the time of randomization). Symptom onset is defined by the “last see normal” principle.

- Informed consent signed

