
Asymptomatic intracerebral hemorrhage
	
an acute extravasation of blood into the brain parenchyma without clinical deterioration. Criteria: evidence of hemorrhage in the brain parenchyma demonstrated by head imaging, surgery or autopsy

Other symptomatic intracranial hemorrhage
	
Any extravascular blood within the cranium associated with clinical deterioration, as defined by an increase of 4 points or more in the score on the NIHSS, or that led to death and that was identified as the predominant cause of the neurologic deterioration. Other Intracranial Hemorrhage is defined as an acute extravasation of blood into the subarachnoid space, epidural space, or subdural space with associated symptoms. Criteria: evidence of hemorrhage in the subarachnoid space, epidural space, or subdural space demonstrated by head imaging, surgery, or autopsy

Other Asymptomatic intracranial hemorrhage
	
An acute extravasation of blood into the subarachnoid space, epidural space, or subdural space without associated symptoms. Criteria: evidence of hemorrhage in the subarachnoid space, epidural space, or subdural space demonstrated by head imaging, surgery, or autopsy

Myocardial infarction with coronary revascularization
	
Evidence of myocardial necrosis in a clinical setting consistent with myocardial ischemia, treated with coronary revascularization. Criteria: The diagnosis of MI will be based on an algorithm developed from the Universal Definition of Myocardial Infarction (Circulation 2007 116:2634-2653) that takes into account 5 categories of clinical information from the acute event: rise and/or fall of cardiac biomarkers, ECG abnormalities, clinical setting, imaging evidence, and pathology.

Myocardial infarction without coronary
	
Evidence of myocardial necrosis in a clinical setting consistent with myocardial ischemia, not treated with

revascularization	coronary revascularization. Criteria: The diagnosis of MI will be based on an algorithm developed from the Universal Definition of Myocardial Infarction (Circulation 2007 116:2634-2653) that takes into account 5 categories of clinical information from the acute event: rise and/or fall of cardiac biomarkers, ECG abnormalities, clinical setting, imaging evidence, and pathology.

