
5. Motor Arm: The limb is placed in the appropriate position: extend the arms (palms down) 90 degrees (if sitting) or 45 degrees (if supine). Drift is scored if the arm falls before 10 seconds. The aphasic patient is encouraged using urgency in the voice and pantomime, but not noxious stimulation. Each limb is tested in turn, beginning with the non-paretic arm. Only in the case of amputation or joint fusion at the shoulder, the examiner should record the score as untestable (UN), and clearly write the explanation for this choice.
	
0 = No drift; limb holds 90 (or 45) degrees for full 10 seconds.
 
1 = Drift; limb holds 90 (or 45) degrees, but drifts down before full 10 seconds; does not hit bed or other support.
 
2 = Some effort against gravity; limb cannot get to or maintain (if cued) 90 (or 45) degrees, drifts down to bed, but has some effort against gravity.
 
3 = No effort against gravity; limb falls.
 
4 = No movement.
 
UN = Amputation or joint fusion, explain: _____
 
5a. Left Arm
 
5b. Right Arm
	
_____
 
_____

Instructions	Scale Definition	Score

6. Motor Leg: The limb is placed in the appropriate position: hold the leg at 30 degrees (always tested supine). Drift is scored if the leg falls before 5 seconds. The aphasic patient is encouraged using urgency in the voice and pantomime, but not noxious stimulation. Each limb is tested in turn, beginning with the non-paretic leg. Only in the case of amputation or joint fusion at the hip, the examiner should record the score as untestable (UN), and clearly write the explanation for this choice.
	
0 = No drift; leg holds 30-degree position for full 5 seconds.
 
1 = Drift; leg falls by the end of the 5-second period but does not hit bed.
 
2 = Some effort against gravity; leg falls to bed by 5 seconds, but has some effort against gravity.
 
3 = No effort against gravity; leg falls to bed immediately.
 
4 = No movement.
 
UN = Amputation or joint fusion, explain: _____
 
6a. Left Leg
 
6b. Right Leg
	
_____
 
_____

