
10. Dysarthria: If patient is thought to be normal, an adequate sample of speech must be obtained by asking patient to read or repeat words from the attached list. If the patient has severe aphasia, the clarity of articulation of spontaneous speech can be rated. Only if the patient is intubated or has other physical barriers to producing speech, the examiner should record the score as untestable (UN), and clearly write an explanation for this choice. Do not tell the patient why he or she is being tested.
	
0 = Normal.
 
1 = Mild-to-moderate dysarthria; patient slurs at least some words and, at worst, can be understood with some difficulty.
 
2 = Severe dysarthria; patient's speech is so slurred as to be unintelligible in the absence of or out of proportion to any dysphasia, or is mute/anarthric.
 
UN = Intubated or other physical barrier, explain: _____ _____
	
_____

Instructions	Scale Definition	Score

11. Extinction and Inattention (formerly Neglect): Sufficient information to identify neglect may be obtained during the prior testing. If the patient has a severe visual loss preventing visual double simultaneous stimulation, and the cutaneous stimuli are normal, the score is normal. If the patient has aphasia but does appear to attend to both sides, the score is normal. The presence of visual spatial neglect or anosagnosia may also be taken as evidence of abnormality. Since the abnormality is scored only if present, the item is never untestable.
	
0 = No abnormality.
 
1 = Visual, tactile, auditory, spatial, or personal inattention or extinction to bilateral simultaneous stimulation in one of the sensory modalities.
 
2 = Profound hemi-inattention or extinction to more than one modality; does not recognize own hand or orients to only one side of space.
	
_____

	
Total NIHSS:
	
_____

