### 5.3 研究人群

#### 入选标准

- 年龄 $\geq 40$ 岁。
- 急性非致残性缺血性卒中（随机化时NIHSS $\leq 3$ 分），且在症状出现的24小时内可以应用研究药物。症状开始的时间定义为“最后看起来正常的时间”。
- 具有中高危卒中风险（随机化时ABCD评分 $\geq 4$ ）的TIA（局灶性脑或视网膜缺血导致的神经功能障碍，并在24小时内完全消失）患者，且在症状出现的24小时内可以应用研究药物。症状开始的时间定义为“最后看起来正常的时间”。
- 已签署知情同意书。

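### The final Chinese and English NIHSS forms differ on which limbs are scored and on how an untestable item is recorded, and no rule says how such an item enters the total.

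*Supplement*

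**What the plan says.** **Untestable items.** English final protocol, Appendix 3, item 10, for a patient who is intubated or physically unable to speak: "the examiner should record the score as untestable (UN), and clearly write an explanation for this choice". Items 5, 6 and 7 use the same UN entry for amputation or joint fusion. The final Chinese protocol, 附表 3, item 10, says "若病人气管插管或其他物理障碍不能讲话,记9分". Chinese items 5 and 6 list 9 as the option for amputation or fusion. Item 7 says in its instructions to record 9, although its own option list runs only from 0 to 2.

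**Limbs rated.** English item 5: "Each limb is tested in turn, beginning with the non-paretic arm"; item 6 says the same for the legs. Chinese items 5 and 6 limit the rating to the affected side, yet print separate blanks for left and right.

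**Total.** Both forms end with a total line, and neither says what to do with 9 or UN when adding up. The SAP (Other Efficacy; Neurological impairment; Data handling conventions) has no rule either.

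**Where the total is used.**
- Entry as minor stroke requires NIHSS of 3 or less in both languages (section 5, inclusion criteria), and 4 or more is an exclusion.
- In Appendix 1, symptomatic intracerebral and other symptomatic intracranial hemorrhage rest on clinical deterioration, "as defined by an increase of 4 points or more in the score on the NIHSS", or on death.
- The Chinese Appendix 1 also uses a rise of at least 4 in criterion (3) of ischemic stroke, which is part of the primary endpoint.
- Change in NIHSS from baseline is an exploratory endpoint.

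**The concern.** The same patient, examined in the same way, can get different totals from the two forms. The cut-offs are small numbers (3 for entry, 4 for deterioration), so a discrepancy of a few points can change a decision.

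The two parts of the problem differ in strength. The affected-side rule is an explicit instruction that contradicts the English form and sits badly with the Chinese form's own left and right blanks. The form also does not define the affected side at follow-up, for example after a TIA that has resolved or when a new deficit appears on the opposite side. The 9 is ambiguous: it may be a code or a score, and nothing written settles which.

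**Working it through.** The plan states no figure on this point, so there is none to reproduce. The check is to add up the total for the same hypothetical patients under each form's written rules.

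**Range of the scale.** The item maxima (1a to 4, then 7 to 11) are the same in both forms: 3+2+2+2+3+3 = 15 and 2+2+3+2+2 = 11. Four limbs at 4 points add 16, so the English maximum is 15+11+16 = 42. With one arm and one leg rated, the Chinese maximum without any 9 is 15+11+8 = 34.

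**Entry: motor points on both sides** (all other items 0).

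| Affected side | Other side | English total | Chinese total |
|---|---|---|---|
| 2 | 0 | 2, eligible | 2, eligible |
| 2 | 1 | 3, eligible | 2, eligible |
| 2 | 2 | 4, excluded | 2, eligible |
| 1 | 3 | 4, excluded | 1, eligible |

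This result does not depend on how a 9 is treated.

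**Deterioration: new deficit on the other side.** Take 2 points on the left at baseline, then 4 new points on the right with the left unchanged.
- English: 2 to 6, a rise of 4, so the rule is met.
- Chinese, left still taken as the affected side: 2 to 2, a rise of 0.
- Chinese, affected side switched to the right: 2 to 4, a rise of 2.
- Chinese, both sides treated as affected: 2 to 6, a rise of 4.

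A stable deficit on the unrated side shifts the entry total but cancels in the change score.

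**Untestable item.** With 0 to 3 points on the other items and one untestable item:
- English, UN carrying no number: 0 to 3.
- Chinese, 9 read as a code and left out: 0 to 3.
- Chinese, 9 added: 9 to 12, above the entry limit of 3.

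An item that becomes untestable after baseline, and is summed as 9, adds 9 to the Chinese change. That alone exceeds 4. An item coded 9 at both visits adds nothing to the change.

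With no untestable item and no motor deficit on the other side, the two totals agree.

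**The case against.** - **The 9 may be only a code.** In items 5, 6 and 10 it lies outside the ordinal range and has a space for an explanation, just as UN does. The Chinese form's introduction also asks for items not assessed to be explained. This stands: a reader might infer that amputees are necessarily excluded, but the text does not tell the examiner to add the 9. It does not tell the examiner to leave it out either, and the English form is equally silent on how UN enters the sum.
- **A 9 cannot make an event.** A reader might infer that intubation alone produces a stroke or a symptomatic bleed. The documents do not support that. Symptomatic hemorrhage needs blood shown by imaging, surgery or autopsy. Chinese progression needs more than 24 hours' duration and new ischemic change on imaging. Stroke and overt bleeding go to an adjudication committee, and hemorrhagic stroke is defined without NIHSS. What remains is the symptomatic or asymptomatic label of a proven bleed, and the NIHSS part of a progression that already shows new imaging change.
- **Only one form may be in use.** All centers are in China, no document says that any site scores with the English form, and investigators are certified in NIHSS. This stands against any claim that sites are shown to score differently from each other. It does not help the reader of the English protocol, who is told that every limb is scored.
- **The affected-side rule is narrow.** It covers items 5 and 6 only; item 7 tests both sides. Exclusion of pre-morbid mRS above 2 limits severe old deficits. This stands, and leaves mainly mild contralateral weakness near the cut-off and new contralateral deficits.

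**Conclusion.** The two final forms conflict, and the scoring rule is incomplete in both languages and in the SAP. The affected-side instruction can by itself move a patient across the entry limit and hide a new deficit from the 4-point rule and the change score. The consequences of the 9 are conditional on its being summed.

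The point is minor. It concerns only patients with an untestable item or with motor points on both sides, probably few, and the documents give no frequency for either, so no size is put on it here. A reader might infer a biased treatment difference in NIHSS change. That does not follow: the same form applied in two blinded arms gives an effect that is equal in expectation, and a shift common to both arms cancels. The exposure is in eligibility, the labelling of events, and some added noise in an exploratory endpoint.

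**What to change.** Reconcile 附表 3 of the Chinese protocol with English Appendix 3: delete the instruction in items 5 and 6 to rate the affected side only, and replace 9 by UN in items 5, 6, 7 and 10.

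Add one derivation rule to the SAP: any stored 9 on these items is treated as untestable and is not summed, and this is applied before totals, changes from baseline and rises of 4 points or more are computed.

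The cost is a correction to one form and one line of data derivation. Sample size, endpoints and the primary model are unaffected.
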